If there is an unforeseen adverse reaction, we would use the usual and customary treatment for iron infusion-associated allergic reactions, which would be no different from response to any other allergic reaction case at the obstetric triage unit. In order to facilitate and create the utmost safety, we would pre-notify the obstetric anesthesiologist on the unit in advance of the scheduled procedure. After the patient completes intravenous iron infusion and has been monitored for at least a total of an hour and has not experienced any adverse side effects, the patient will be advised to present herself for the ferumoxytol-MRI. The coordination for this will be provided by the study coordinator assigned to the study.

The vast majority of serious allergic reactions occur within short time (10 minutes) of starting the infusion. No reactions have been reported after 30 minutes of infusion. We have arbitrarily extended observation period to one hour and no one is expected to develop allergic reactions after that time.

Patients have hemogram done routinely for clinical care at 28 weeks. We will perform a panel of iron study (serum iron and transferrin levels) two-three weeks after the day of infusion. TIBC is not useful in settings of patients having received iron infusion, hence is not included in the panel.

Concomitant Therapy

There are no prohibited concomitant medications, therapies or supplements.

STUDY VISITS AND PROCEDURES

The procedures performed at each study visit are listed in the table below.

Procedure	Screening	Visit 1	Visit 2	Visit 3	Delivery	End of Study/ Postpartum
Visit Window	28 0/7 – 34 6/7 wk GA	29 0/7 - 35 6/7 wk GA	29 3/7 - 36 4/7 wk GA	2-3 wk after ferumoxytol		Delivery + 6 wks
Informed Consent	X					
Review Eligibility Criteria	X					
Demographics	X					
Review Concomitant Medications	X	X	X		X	X
Medical History	X				X	
Vital Signs		X	X			
Ferumoxytol Administration		X				
MRI		X	X			
Biological specimen collection	X				X	
Adverse Events Review/ Assessment		X	X	X	X	X
Iron Panel				X		

Screening and Enrollment

Informed Consent

Patients who express interest in the study will be referred to study personnel, who will discuss the protocol, including all procedures that will be administered as part of this research, the risks associated with participation, and the timeline for all research visits. Any questions concerning study participation will be answered before written consent is

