The second visit and MRI will occur 3-5 days after visit 1. This visit could occur anytime between 29 3/7 - 36 4/7 weeks gestation at the locations listed above. The purpose of the second MRI to detect implantation sites for macrophages after ferumoxytol is cleared from the body. This procedure will only last 60 minutes.

The study coordinator will perform all the following procedures:

- All FGR diagnosis data will be reviewed and collected.
- Subjects will be scheduled for a 60-minute MRI and adverse event review.
- A medical record review will follow the subject's regularly scheduled visit.

Visit #3: Iron Panel (Blood draw)

We will perform a panel of iron study (serum iron and transferrin levels) two-three weeks after the day of infusion. This visit will occur at any time between 2-3 weeks after the ferumoxytol infusion. Every effort will be made to have this visit coincide with a standard of care visit, but in the event this cannot happen within window, a research only visit will be created.

- Blood collection will be performed by phlebotomy staff at UPH-Meriter Hospital, blood sample will be sent to Meriter Labs for analysis.
- Results will be uploaded to the subject's medical record.

Delivery Visit (time of delivery)

The procedures performed for research purposes only include:

- Blood/urine collection, will be performed as a paid service by nursing or phlebotomy staff at UPH-Meriter Hospital. This procedure should last only five minutes.
- maternal and newborn medical record review, will be performed by the study coordinator
- The findings from the placenta pathology report will be used to correlate with MRI findings. There will be no placental collection. The study coordinator will review the pathology report from the subject's medical record.

The standard of care procedures will include delivery of the baby and all associated procedures, performed by clinical staff.

Postpartum Follow-up

This follow-up is for research purposes only and will be performed by the study coordinator. The phone call should not last more than 15 minutes.

- Follow-up Phone Call (any time post-delivery, up to 6 weeks postpartum)
- Adverse event review with subject.
- Review of Concomitant medication

STATISTICAL CONSIDERATIONS

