Definitely Related: An AE categorized as Definite is clearly related to the intervention. If the timing of the AE is definitely consistent with the exposure to the study intervention and it is most likely that the AE was caused by the study intervention such as because a high occurrence of the AE was expected based on the study intervention materials? In this case, the PI may categorize the AE as definitely related.

Probably Related: An AE that is likely related to the use of the drug. A Probable AE is likely related to the intervention. If the timing of the AE is consistent with the exposure to the study intervention and it is more likely that the AE was caused by the study intervention than not, the PI may categorize the AE as Probable.

Possibly Related: An AE that may be related to the use of the drug. If the timing of the AE is reasonably consistent with the exposure to the study intervention, and there is another cause of the AE that could be equally likely, the PI may categorize the AE as Possible.

Unlikely Related: An Unlikely AE is one that is doubtfully related to the intervention. The coincidence of the AE with the exposure of the investigational product or intervention should be assessed. An AE that continued while the intervention was interrupted or stopped, or if the AE resolved while the intervention continued, may be categorized as Unlikely. If there is another more likely cause of the AE, the PI may determine that the AE was unlikely related to the study intervention.

Not Related/Unrelated: An Unrelated AE is one that is clearly NOT related to the intervention. An AE may be considered Unrelated if the subject did not receive the study intervention or if there is another obvious cause of the AE (for example, a car accident or other disease/condition).

Adverse Events of Special Interest

Adverse events pertaining to the subject (mother) or neonate child occurring after the signing of consent until 6 weeks post-delivery, will be collected. Conditions that are

routinely encountered by obstetricians or pediatricians, such as C-section or infant jaundice, will be recorded on the adverse event log, but will not be reported (i.e. entered into OnCore) per clinical investigator's judgement. All adverse events meeting the HS-IRB reportable event requirements will be entered into OnCore, regardless of being considered a routine condition.

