Adverse events that are expected in pregnancy and assessed as not related/unrelated to the protocol will not be reported to the ICTR DMC and entered into OnCore. These events include but are not limited to nausea and vomiting, dizziness, abdominal discomfort, back pain, vaginal discharge, and Braxton Hicks contractions.

Given the exclusion criteria and MRI screening, we do not anticipate any major events related to the MRI procedure. However, it is possible that patients report claustrophobia or anxiety in the large bore MRI machines. This may potentially require that we reduce the BMI cutoff from 39.9 Kg/m² to a lower value for the purpose of our study examination. The adverse response and claustrophobia concerns, even in a wide bore MRI research equipment, is one of the reasons we are choosing the BMI range of 18.5-39.9 Kg/m² for our study purposes.

Any planned hospitalizations for the delivery will not be reported as an SAE, but if any AE occurs during delivery or if the hospitalization is lengthened due to safety concerns this will be reported.

Genetic conditions, birth defects, or cardiac defects not recorded or suspected prior to consent will be documented as adverse events.

Any event may be documented and followed for up to 1 year post-delivery upon investigator's discretion.

Serious Adverse Event Reporting Requirements

Adverse Events that are:	Notify HS IRB	Notify DMC	Notify FDA** (events related to Ferumoxytol-MRI only)
Serious Suspected/Related* Unexpected	Within 14 business days	Within 14 business days	Notify FDA and all participating institutions as soon as possible, but no later than 15 calendar days after learning of the event
Serious Life threatening or Fatal Suspected/Related* Unexpected	Within 1 business day (24 hours) of learning of the event.	Within 1 business day (24 hours) of learning of the event.	Within 7 calendar days of learning of the event

* The UW-Madison HSIRB requires immediate reporting of serious adverse events that are probably or definitely related, whereas the FDA requires reporting of these events that are possibly, probably or definitely related. Therefore if an event is reported to the HSIRB, the event will also be reported to the FDA.

Reporting requirements to the ICTR Data Monitoring Committee

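### The postpartum adverse event call has no earliest day, so nothing scheduled guarantees a review at the end of the 6-week collection window

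*Combined protocol and SAP*

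**What the plan says.** Three places in the protocol bear on when adverse event collection ends.

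- Adverse Events of Special Interest sets the window: "Adverse events pertaining to the subject (mother) or neonate child occurring after the signing of consent until 6 weeks post-delivery, will be collected".
- Postpartum Follow-up describes one telephone contact by the study coordinator: "Follow-up Phone Call (any time post-delivery, up to 6 weeks postpartum". Its content is "Adverse event review with subject" and a check of concomitant medication. No earliest day is given and no second contact is listed.
- The table under Study Visits and Procedures heads its last column "End of Study/ Postpartum", gives it the window "Delivery + 6 wks" and marks adverse event review in it. No column follows, and no tolerance is stated.

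Other provisions could bring later events to light. The Delivery Visit section lists "maternal and newborn medical record review, will be performed by the study coordinator". The Research Procedure Descriptions include a separate item on obtaining clinical data from records, which covers neonatal outcome and maternal complications. The Data and Safety Monitoring Plan has pregnancy outcome documented and reviewed after delivery. Adverse Events of Special Interest also says "Any event may be documented and followed for up to 1 year post-delivery", at the investigator's discretion.

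**The concern.** The collection window has a fixed end, but the only scheduled postpartum contact can fall anywhere inside it. A coordinator who telephones in the first days after delivery has followed the protocol, and no later adverse event review is planned for that woman. Observed time after delivery could then run from almost nothing to the full 6 weeks, depending only on when the call happened to be made.

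What is at stake is the completeness and evenness of the safety data. The protocol itself says that data on ferumoxytol risk in pregnancy are lacking (Risks and Benefits, Study Drug). It reports that the hospital could not supply pregnancy outcomes for women it had previously given the agent. It also lists serious neonatal complications to which growth-restricted pregnancies are prone (Preeclampsia and FGR Risks). Outcome safety data from these 20 women are therefore a useful product of the study. The definition of an adverse event does not depend on a suspected link to the intervention, so a late event counts under the protocol's own terms even if it is unlikely to be drug-related.

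**Working it through.** The plan has no figure of its own to reproduce here, since no sample size, power or event rate is involved. The check compares the window with the permitted call days, and then asks whether another provision closes the gap.

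**Inputs**

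- Length of the postpartum window: 6 weeks × 7 = 42 days, counting delivery as day 0 (Adverse Events of Special Interest).
- Permitted call day *d*: any day from 0 to 42 (Postpartum Follow-up).
- Scheduled adverse event reviews after the call: none (visit table).

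**Formula.** Days without a scheduled review = 42 − *d*; share of the window = (42 − *d*)/42.

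| Call day | Days left | Share of window |
|---|---|---|
| 7 | 42 − 7 = 35 | 35/42 = 83% |
| 14 | 42 − 14 = 28 | 28/42 = 67% |
| 21 | 42 − 21 = 21 | 21/42 = 50% |
| 42 | 42 − 42 = 0 | 0% |

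Every row complies with Postpartum Follow-up. The call days are illustrations, because the documents give no distribution. If calls were spread evenly over the window, which is an assumption, the average gap would be 42/2 = 21 days.

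**The two readings of the table**

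- If "Delivery + 6 wks" means a contact at week 6, the table agrees with the collection window but conflicts with Postpartum Follow-up, which permits an earlier call.
- If it means no later than week 6, the table agrees with Postpartum Follow-up, but then no scheduled procedure guarantees that collection runs to the end of the window.

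The texts need reconciling on either reading.

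**Other sources of late events**

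- Record review is listed at Visit 2 and at delivery. The general item on obtaining clinical data from records has no date.
- Primary Source Documents makes hospitalization and emergency records source data where applicable, and adds the mother's and newborn's hospital records. This says what counts as a source. It does not say that anyone looks at week 6.
- Outcome review under the Data and Safety Monitoring Plan is placed after delivery, without a date.
- Follow-up to 1 year is discretionary and is not a scheduled contact to find new events.
- The triage alert in the Research Procedure Descriptions concerns admissions of pregnant women, so it does not cover this period.

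Any of the first four may reveal a later event. None is a review dated to the end of the window.

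**The case against.** The strongest reply is that the duty to collect events until 6 weeks stands whatever the day of the call. A reader might infer that an early call closes follow-up. No sentence says so; the idea comes from the last column's heading and the absence of a later contact. An early call satisfies one section without cancelling the other. This part of the reply stands, and the point is limited accordingly: what is missing is a scheduled review at the end of the window, not the obligation to collect.

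It is also fair to say that the interview is not the only source of events and that record review is not confined to the delivery visit. That stands too, but it does not close the gap, because those sources are undated or discretionary.

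A reader might go further and conclude that a reported 6-week event rate would be wrong, or that one missed serious event in 20 women would shift it by 1/20, or 5 percentage points. The documents do not support this. Statistical Considerations plans no safety endpoint or event rate, only correlation of imaging with pathology. The Data Monitoring Committee section describes a summary of the number and seriousness of events. There is no comparison arm. The 1/20 figure would be the same for any event in 20 women and does not measure this defect. The study stopping rules concern MRI-related claustrophobia or anxiety and anaphylaxis, not late postpartum events.

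Finally, moving the only call to 6 weeks carries some risk of not reaching the woman at all. That is a real cost, and the fix addresses it.

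**Conclusion.** The mismatch is real and minor. The protocol promises collection over 42 postpartum days, permits the only postpartum adverse event contact on any of them, and schedules nothing later. The part of the window without a scheduled review can be anything from 0 to nearly 42 days per woman, so ascertainment may be incomplete and may differ between women for no reason other than the day of the call.

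This rests on two things: the absence of any later contact in the visit table or visit descriptions, and the absence of a date on the record-based sources. It does not rest on any assumed distribution of call days, and no number of missed events can be estimated from the documents. The correlation of MRI findings with placental pathology is unaffected.

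**What to change.** Bring Postpartum Follow-up, the last column of the visit table and Adverse Events of Special Interest into line.

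- Schedule the call at or shortly after 6 weeks postpartum, and state in the table that this is a time point, with a tolerance.
- Have the call ask about maternal and neonatal events up to 6 weeks.
- If a woman can only be reached earlier, record the call date and check the maternal and newborn records at 6 weeks.
- When adverse events are summarized, show the date of the last adverse event review for each woman so that any unequal observation is visible.

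With the call at or after day 42, the days without a scheduled review fall to 0 of 42. The number of calls stays the same, and sample size, imaging and study treatment do not change. The cost is a wording amendment, a record check for women reached early, and slightly more loss to contact at 6 weeks, which the record check partly offsets. If the team prefers to keep the flexible call, a dated record check at 6 weeks for every woman would be the smaller repair, though it would miss events that never reach those records.

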This is an exploratory investigation of placental lesions identification by MRI and there is not data available to provide sample size justification. The goal of this sub-project is to expand the scope of our project to asses human placenta function in on-going pregnancies. Expanding the project to include women with diagnosis of FGR as per our discussion with NICHD program officer and NICHD-HPP scientific leadership was granted to us and will allow us to develop robust preliminary data for future NIH grant application. Our plan is to conduct MRI imaging and correlate the findings with placental pathology findings. We request permission to approach 60 subjects and anticipate to study a total of 20 subjects: this will provide adequate data to define future direction of this research.

RISKS AND BENEFITS

Potential direct benefits to subjects.

Results from the MRI scans will be uploaded to the subjects' EMRs. The study PI will also share the results with the subject's primary obstetric physician and will provide appropriate counseling to the subject. The clinical investigator, [name] is a Maternal-Fetal Medicine (MFM) specialist who can explain the findings of the MRI imaging and may help to reduce the subjects' anxiety. A recommendation to increase clinical monitoring may be made by the study PI based on MRI findings.

The PI will personally discuss imaging results with the clinician who is providing direct care to subject in question. The subject's primary care clinician will be involved in the discussion with subjects regarding study MRI results and any additional recommended follow-up (e.g., added subject/fetal growth monitoring). However, it will be the provider's decision if they want to take the findings of the study into consideration to make any modifications in the patient's clinical care and monitoring.

The current standard of care for FGR cases consist of increased monitoring in the following manner: non-stress test (NST) performed 2 times per week, Doppler velocimetry performed 1 time per week, and growth ultrasound performed 1 time per month after the diagnosis of FGR until delivery. Depending on the clinical manifestations, the clinicians may decrease or increase monitoring frequency for the ultimate goal of preventing perinatal mortality and morbidity. Fetal monitoring frequency will not be increased solely based on findings from the study, but rather taking into consideration other factors regarding maternal and fetal health.

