MFM clinicians use multiple tests to determine the course of care in high-risk pregnancies. The use of study results from MRI findings would only confirm standard of care decisions and not directly influence clinical care. It is not unreasonable to connect investigational imaging method knowledge to pre-existing knowledge.

The only current method to detect placental lesions is through pathologic examination of the placenta after delivery. It has been well documented that FGR fetuses with confirmed placental lesions have worse post-natal outcomes than those whose placental lesions are not confirmed. The purpose of the proposed study is to detect placental lesions before the fetus is born in an effort to come up with a better treatment plan to improve neonatal outcomes. The MRI has the potential to indicate which fetuses, based on presence or absence of placental lesions, will have a better or worse outcome at delivery. The MRI would be one of many tests taken into consideration when determining best clinical management of patients with FGR diagnosis.

The following benefits are anticipated.

1. Potential to confirm that there are no perfusion defects and no evidence of macrophage recruitment in the placental bed. This would be enormously reassuring to the subjects, particularly the absence of perfusion defects.

2. If perfusion defects or recruitment of macrophages in the placental bed are detected, we would recommend the following modifications to their clinical care.
 - a. If fetal growth is not already being monitored, we would recommend to the clinic that additional monitoring be added to clinical care.
 - b. The number of visits for patients would be increased to monitor for development of new or acceleration of hypertension, indicative of pre-eclampsia.
 - c. Depending on the severity of placental lesions, we may inform to clinicians to which patients may require earlier delivery.

In this context, these three modifications will empower clinicians to provide individualized care based on novel advanced and sophisticated imaging information.

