[name], PhD, [name] and [name]. The MRI research team will analyze and interpret the findings of the MRI imaging to determine if macrophages are detected in the uterine wall. The study PI, [name], and [name] will make the final decision for interpretation of the MRI imaging.

The PI will provide appropriate counseling to the subject and their primary obstetrician, as he is a Maternal-Fetal Medicine (MFM) specialist who can explain the findings and to reduce the subjects' anxiety. [name] is a UW Ob/Gyn physician, working in the UPH-Meriter Perinatal Clinic who routinely reviews MRI scans and counsels patients with at-risk pregnancies. [name] is the most qualified physician-scientist in the region to explain to the subject the meaning of the findings and how she will be monitored.

The study PI will disclose results from the MRI scan to subjects. The primary finding will be the presence or absence of macrophages at the maternal-fetal interface at the site of implantation. If we observe other changes in the placenta, such as lack of perfusion in intervillous space, we will also report this finding. The PI will discuss these findings with the subject in layman's terms and describe the modifications in clinical care as a result of these findings.

Interpretation of clinical monitoring will be enhanced based on MRI findings.

We may confirm that there are no perfusion defects and no evidence of macrophage recruitment in the placental bed. This would be enormously reassuring to the subjects, particularly the absence of perfusion defects. However we will not suggest to the clinician to change the course of monitoring.

If we detect perfusion defects or recruitment of macrophages in the placental bed, we would suggest that these subjects have following modification in clinical care.

- a. If fetal growth is not already being monitored, we would recommend to the clinic that additional monitoring be added to clinical care.
- b. The number of visits for patients may be increased to monitor for development of new or acceleration of hypertension, indicative of pre-eclampsia.
- c. Depending on the severity of placental lesions, we may inform clinicians as to which patients may require earlier delivery.

In this context, these three modifications will empower clinicians to provide individualized care based on novel advanced and sophisticated imaging information.

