Review of MRI by the MRI research team will occur within one week and an appointment for counseling for the subject would be scheduled within the following week. This timeline of counseling the subject within 2 weeks is safe given that a) the subject is already being monitored for the emergence of disease diagnosis and, b) we are detecting placental lesions that are premonition of emergence of severe fetal growth restriction or preeclampsia, which are not likely to occur until 4-8 weeks after the infusion MRI.

The PI, a physician at the Center for Perinatal Care clinic, will have a face to face research visit with the subject about their MRI findings. PI will also contact with the subject's physician to discuss the results. This will occur within two weeks of the last MRI scan.

Results from the MRIs will be made available in the subject's medical record.

Blood and urine samples collected for analysis will not provide clinical information, this is pioneering work and no clinical data exists for this kind of work.

DATA COLLECTION, HANDLING, AND RECORD KEEPING

Privacy/Confidentiality

The paper research records will be kept confidential. The results of this study may also be used for medical and scientific publications, but the subject will not be identified personally in any presentations or reports related to this research.

The information collected from subjects and from their medical records will be used by the researchers and research staff of the UW-Madison and its affiliates (the University of Wisconsin Hospital and Clinics and the University of Wisconsin Medical Foundation) for this study. It may also be shared with others at the UW-Madison.

Any paper documentation including the consent form will be kept in the UW Ob/Gyn clinical research office (located at McConnell Hall) and locked in a cabinet. The consent form will be stored in a separate file cabinet from the patient data. There is limited access to the office and only the study coordinators have a key to the locked files.

Patient information that is entered into the database stored on department servers will be coded; only the investigators involved in this study will have access to the research-related information. Results from this study may also be used for medical and scientific publications, but the subject will not be identified personally in any presentations or reports dealing with this research.

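### The protocol says study MRI will not directly influence care, yet lists care changes for MRI-positive women, and the available text has no safeguard for the MRI-pathology comparison

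*Combined protocol and SAP*

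**What the plan says.** Three places bear on whether the study MRI may change care.

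- **RISKS AND BENEFITS, Potential direct benefits to subjects.** The principal investigator may recommend closer monitoring because of the MRI, and the treating provider decides whether to act. The text adds "Fetal monitoring frequency will not be increased solely based on findings from the study", and the same sentence says other maternal and fetal factors are weighed. It then states: "The use of study results from MRI findings would only confirm standard of care decisions and not directly influence clinical care".
- **Same section, anticipated benefits, item 2.** If the MRI shows a perfusion defect or macrophage recruitment, the team would recommend three modifications: growth monitoring where none is in place, extra visits ("The number of visits for patients would be increased to monitor for development of new or acceleration of hypertension"), and, depending on lesion severity, advice to clinicians about earlier delivery.
- **Later text on interpreting and disclosing the MRI, just before DATA COLLECTION, HANDLING, AND RECORD KEEPING.** The same list returns, but extra visits now *may* follow where item 2 says they *would*. On delivery, "we may inform clinicians as to which patients may require earlier delivery". The investigator is to explain to the woman how her care changes because of the scan. If the MRI is clear, no change in monitoring is to be suggested. Counselling takes place within two weeks of the last scan.

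On the record and the reference standard: "Results from the MRIs will be made available in the" subject's medical record, and the Privacy/Confidentiality text confirms this. Under Delivery Visit, "The findings from the placenta pathology report will be used to correlate with MRI findings", and the coordinator takes that report from the medical record. STATISTICAL CONSIDERATIONS names this correlation as the plan, says that "there is not data available to provide sample size justification", and gives the size: investigators "anticipate to study a total of 20 subjects".

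**The concern.** A clinician or ethics board cannot tell from this text whether a positive study MRI is meant to change care. The MRI is not validated (the protocol itself says women will be told it is not yet a diagnostic tool), and the statements concern visits and delivery timing in pregnancy.

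The statistical consequence follows from the same text. The one planned analysis compares MRI with placental pathology. If MRI-positive women are managed differently because of the MRI, the gestation at which the placenta is examined becomes partly a result of the test. So do gestational age at delivery, birth weight, neonatal outcome and diagnosed preeclampsia, all of which are collected. If the pathologist knows the MRI result, the reference is no longer independent of the index test. An influence that is not recorded when it happens may not be recoverable later, and these data are intended to support a grant application.

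**Working it through.** No sample-size, power or error-rate figure bears on this point, so there is nothing of the plan's to reproduce. The check is a comparison of texts, followed by arithmetic on when results become known.

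**Step 1. The statements side by side**

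| Topic | MRI does not drive care | MRI prompts a change |
|---|---|---|
| Care in general | "The use of study results from MRI findings would only confirm standard of care decisions and not directly influence clinical care" | Item 2: modifications would be recommended if MRI is positive |
| Visits | No separate statement | *Would* increase (item 2); *may* increase (disclosure text) |
| Delivery | No separate statement | "we may inform clinicians as to which patients may require earlier delivery" |
| Fetal monitoring | Not increased *solely* on study findings | Investigator may recommend more monitoring because of the MRI |

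The first row is the clear contradiction, and both sides of it stand in the same section. The second row is a separate inconsistency. The last row can be reconciled through the word *solely* and the provider's discretion.

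**Step 2. Does care depend on the index test?** Yes, as written. The listed recommendations follow a positive MRI, and no change is suggested after a clear one. All 20 women are to be told their result, so there is no undisclosed group for comparison.

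**Step 3. Is the result known in time to matter?**

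- Last MRI: 3 to 5 days after the infusion visit (Visit #2).
- Counselling: up to 14 days after the last MRI.
- Latest disclosure: 3 + 14 = day 17 to 5 + 14 = day 19.
- Severe growth restriction or preeclampsia is expected 4 to 8 weeks after the infusion MRI, which is day 28 to day 56.
- Lead time before that window opens: at least 28 − 19 = 9 days. Before it closes: up to 56 − 17 = 39 days when disclosure is on day 17.
- By gestation: Visit 2 at 29 3/7 to 36 4/7 weeks, plus 2 weeks, gives disclosure by 31 3/7 to 38 4/7 weeks. Some women scanned late could deliver before disclosure.

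For women still undelivered, the result arrives early enough to affect visits, detection of hypertension and timing of delivery.

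**Step 4. Which way would bias run?**

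- A pathologist aware of the MRI would tend to raise MRI-pathology agreement.
- Earlier delivery of MRI-positive women could act either way. It leaves less time for lesions to develop, which could lower agreement. It also brings pathology closer in time to the scan, which could raise it.
- The effect on recorded outcomes is more direct. If advice on earlier delivery is followed, gestational age at delivery falls because of the MRI.

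**Step 5. How large?** This cannot be computed. It would need the MRI-positive rate, the rate at which providers act on recommendations, and the resulting shift in delivery date. The documents give none of these.

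**The case against.** The strongest reply is that the text describes a team that advises and a provider who decides. The fetal-monitoring sentence says *solely*. The extra visits are for maternal hypertension, which is a different matter. Growth monitoring is recommended only where it is absent, and the protocol says all these women already have it. MRI is described as one input among several, and on delivery the team only *may inform*. The study is exploratory, with 20 women and no formal outcome endpoint.

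Most of this stands, and it narrows the point. A reader might infer that the fetal-monitoring sentence is flatly contradicted, or that the protocol commits to MRI-driven delivery; the wording supports neither. What remains is the statement that MRI will not directly influence care, set above MRI-triggered recommendations, together with *would* against *may*. Discretion does not reconcile either of these.

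A reader might also infer that the bias must inflate agreement. The documents do not support that: only pathologist awareness has a likely direction, and nothing says the pathologist consults the MRI. Research images are also filtered on the imaging archive to keep them apart from clinical data, although results are still posted to the record.

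Finally, a reader might use the protocol's 40% or 60% as an MRI-positive rate. The 40% is the share of cases that are constitutionally small, and the 60% is the error rate of clinical diagnosis. Neither is an MRI-positive rate.

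**Conclusion.** The contradiction is established from current text and must be reconciled before the protocol can be followed consistently. The risk to the MRI-pathology comparison is a sound inference, not a demonstrated bias. It rests on three facts: recommendations go only to MRI-positive women, results are disclosed during pregnancy, and the MRI result and the reference report sit in one record. Its size is unknown, and for delivery timing so is its direction.

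The available text describes no masking of the pathologist, no MRI read formally finalised before delivery, and no record of MRI-driven decisions. Some text on MRI interpretation was not available, so this is an absence from what could be read. MRI review is due within one week, so most reads will probably precede delivery, but no formal lock is stated.

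The exploratory purpose limits the statistical consequence. It does not excuse conflicting statements about care.

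**What to change.** 1. Reconcile the two passages in RISKS AND BENEFITS and the later disclosure text into one statement on whether and how study MRI results may affect care, including *would* against *may*. The sponsor decides its content.
2. Finalise and date the research MRI read before delivery, and keep the MRI result off the placental pathology request. This reduces awareness but does not guarantee masking, because the result is in the record; the report should say so.
3. Add a case-report-form item for any care change or delivery decision that the clinician attributes to the MRI. Report those women, and the MRI-to-delivery interval, descriptively. Do not exclude them: recommendations go only to MRI-positive women, so exclusion would remove only MRI-positives and could empty that group in a sample of 20.
4. Do not present MRI-outcome associations as prognostic validation where the MRI influenced care.

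The cost is protocol wording, one form item and a little extra reporting. Disclosure to women can continue, and no procedure is added.
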